Concurrence of fasting with pregnancy as a physiological condition introduces some controversies regarding the condition of the mother and the fetus. Pregnant women are exempt from fasting if it poses a risk to the fetus; however, many still fast while others are more cautious about its practice. Many pregnant show great interest in fasting and are able to perform this religious practice; however, they are concerned about their fetus and inquire about the possible associated complications during pregnancy According to the statics, in West Africa, 90% of pregnant women fasted during the month of Ramadan. The prolonged hunger presents itself as hypoglycemia or hyperketonuria, which may affect the neonatal weight, neonatal mortality and disability. During fasting, pregnant and breastfeeding women experience changes in metabolism, sleep patterns and daily physical activity (*Cuningham et al., 2010*).

Most Muslims observe Ramadan every year. Exemption from fasting is permitted for women who are pregnant or breastfeeding, but the missed fasts must be completed before the next Ramadan (**Rashed, 2010**).

Muslim women choose to fast during pregnancy because of a sense of religious duty, familial support, positive views on fasting, and difficulty in completing the missed fasts at another time. A previous study found that Muslim women believed the only reason not to fast would be perceived harm to mother or fetus, but that fasting during pregnancy is safe for healthy women. Women feel strong spiritual, emotional, physical, and social benefits from fasting; it is seen as a way of maintaining cultural identity and unity among their communities (**Robinson et al., 2005**).

Many women asking their obstetrician if fasting is safe for their baby or not? There have been many studies on metabolic changes and different aspects of human health during and after Ramadan, but there have been few studies on the effect of fasting on pregnancy outcome and there are also some controversies in the findings of different studies (**Ziaee et al., 2006**).

Ramadan fasting during pregnancy is a controversial issue. A group of pregnant women do not fast due to the probable harmful effect on fetal health. Although Ramadan fasting may be postponed to the postnatal period, some pregnant women obey it as a religious activity (*Joosoph, 2004*).

There are several reports regarding the effects of Ramadan fasting on the human metabolism. Fasting leads to a decrease in serum glucose, insulin, lactate, and carnitine, as well as an increase in free fatty acids, hydroxy butirate, cholesterol, and triglyceride levels. As we know, maternal glucose infusion causes stimulation of short-term fetal activity and uteroplacental blood flow is essential for fetal development and wellbeing (*Osol, 2009*).

During the month of Ramadan, healthy adults abstain from food and drink from dawn to sunset. Pregnant are allowed, if they choose, to postpone the fast until after delivery. However, most of the women would like to fast with their families rather than doing this alone later. Therefore, most Muslim pregnant women fast during the holy month of Ramadan. Consequently, diet restriction and fasting could adversely affect pregnancy outcome, especially if Ramadan

*The Effect of 3rd trimester Ramadan fasting on Obstetric outcome
(Study Protocol)*

falls during the hot summer months with long days of fasting
(Mirghani, 2006).

Aim of the Work

This study aimed to find out the association between fasting during Ramadan and obstetric outcome in third trimester regarding to hypoglycemic symptoms, fetal growth, AFI, mode of delivery, birth weight and neonatal outcome.

Study question:

In pregnant women in the third trimester, does fasting during the holy month of Ramadan has a poor obstetric outcome regarding to hypoglycemic symptoms, fetal growth, AFI, mode of delivery, birth weight and neonatal outcome?

Patient and Methods

Type of the study :

Prospective Comparative Cohort Study.

Study setting :

EL- Demerdash outpatient clinic.

Duration of the setting :

The Holy month of Ramadan (from 18th June To 16th July 2015. Avenge hours of fasting 16 hours.

Population (study will include):

The patients will be recruited from outpatient clinic during Ramadan then followed during the holy month then grouped into three groups A ,B, C regarding fasting state and each group contain 53 patient after exclusion drop out patient

A- Non fasting group

B- Partially fasting group (average days of fasting 10-20 day).

C- Totally fasting group

Inclusion criteria:

- *Within the range of 20 – 35 years.*
- *3rd trimester pregnancy (starting from 28 weeks) which is going to be calculated according to the date of the last menstrual period & confirmed by ultrasonography.*
- *Normal healthy women with average body mass index (BMI). Normal range (18.5 to 25).*
- *Women included have no medical disorder.*

Exclusion criteria :

- *History of systemic disorder.*
- *Smoking narcotics or alcohol use.*
- *Have previous history of fetal loss.*
- *Multiple pregnancies.*

Methodology

Women who fulfilled the eligibility criteria are going to be subjected to:

1) Complete history taking:

- a. Personal history.*
- b. Medical history.*
- c. Obstetric history.*
- d. History of present pregnancy: with special emphasis on signs & symptoms of hypoglycemia in the form of fatigue, dizziness, fainting, blurred vision, vomiting.*
- e. Fetal kicks.*

2) General examination: assessment of vital data.

3) Ultrasound fetal biometry every 2 weeks till delivery looking for

- **Fetal biometry.**
- **AFI (ammonic fluid index)**
- **Doppler.**

4) Fetal weight after delivery.

Sample Size Justification:

*The required sample size has been calculated using the G*Power Software (Universität Düsseldorf, Germany).*

The primary outcome measure is the difference between the three study groups as regards the fetal birth weight. The secondary outcome measures are the incidence of unwanted fetal outcomes (e.g., IUGR, PTL, or NICU admission).

Since there is currently no adequate information regarding the outcome measures in patients who are fasted for the whole or part of the month, the current exploratory study would target an effect size that could be clinically relevant.

So, it is estimated that a sample of 53 patients in each study group (total 159 patients) would achieve a power of 80% (type II error, 0.2) to detect a statistically significant difference among the three groups as regards the fetal birth weight for a medium effect size (eta squared, η^2) of 0.25. The effect size (eta squared, η^2) is calculated as follows: $\eta^2 = \text{between-group sum of squares} / \text{total sum of squares}$. This calculation used a two-sided F test with a numerator degree of freedom ($k-1$) of 2, a denominator degree of freedom ($n-k$) of 156, and a confidence level of 95% (type I error, 0.05), where k is the number of groups and n is the total sample size. This sample size of 159 patients would achieve a power of 93% (type II error, 0.07) to detect a statistically significant difference among the three groups as regards the secondary outcome measures (IUGR, PTL, and NICU admission) for a medium effect size (w) of 0.3. The effect size (w) is calculated as follows: $w = \sqrt{(\chi^2/N)}$, where χ^2 is the chi-squared statistic and N

is the total sample size. This calculation used a two-sided chi-squared test with a confidence level of 95% (type I error, 0.05).

A medium effect size of $\eta^2 = 0.25$ or $w = 0.3$ for the primary or secondary outcome measures, respectively, has been chosen as it could be regarded as a clinically relevant difference to seek in this exploratory study.

Assuming an expected drop-out rate of approximately 10%, a total sample size of 180 patients (60 patients per group) will be recruited.

Statistical Methods:

Data will be collected, tabulated, then analyzed using IBM© SPSS© Statistics version 22 (IBM© Corp., Armonk, NY).

Normally distributed numerical data will be presented as mean and SD, and skewed data as median and interquartile range. Qualitative data will be presented as number and percentage. Comparison of normally distributed numerical data will be done using one-way analysis of variance (ANOVA). Skewed data will be compared using the Kruskal Wallis test. Categorical data will be compared using the chi-squared test, or Fisher's exact test when appropriate. A two-sided p-value <0.05 will be considered statistically significant.

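### Groups are formed after follow-up from the fasting actually done, so women who stop because of symptoms or a worrying scan can be moved from the total-fasting group into the partial-fasting group

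*Combined protocol and SAP*

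**What the plan says.** All references are to the combined protocol and SAP.

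- **Timing of grouping (Population).** "The patients will be recruited from outpatient clinic during Ramadan"; they are "then followed during the holy month then grouped into three groups A ,B, C regarding fasting state". Group membership is thus settled by behaviour during follow-up.
- **Group definitions (Population).** A is non-fasting and C is total fasting, neither with a day limit. The partial group is given as "B- Partially fasting group (average days of fasting 10-20 day".
- **Monitoring (Methodology, items 1 and 3).** The history puts special emphasis on symptoms of hypoglycaemia. Scans are specified as "Ultrasound fetal biometry every 2 weeks till delivery looking for" biometry, amniotic fluid index (AFI) and Doppler.
- **Outcomes (Aim of the Work).** "hypoglycemic symptoms, fetal growth, AFI, mode of delivery, birth weight and neonatal outcome". Birth weight is primary (Sample Size Justification).
- **Reasons not to fast (introduction).** "Pregnant women are exempt from fasting if it poses a risk to the fetus", and an earlier study is reported as finding that "Muslim women believed the only reason not to fast would be perceived harm to mother or fetus".
- **Analysis (Statistical Methods).** One-way ANOVA or Kruskal-Wallis for numerical data, and chi-squared or Fisher's exact test for categorical data, all unadjusted.

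The plan does not call for a record of intended fasting, of the date of stopping or of the reason for it. It has no analysis by intended or time-varying exposure.

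**The concern.** The exposure is fixed only after events that are themselves outcomes, or early signs of outcomes, have had the chance to change it. Take a woman who begins Ramadan fasting every day and stops on day 14 after fainting or after a scan showing low AFI. She meets the definition of group B. Had she felt well, she would have been in C. If women like her stop more often than others, C is left with a more favourable selection of women and B receives the less favourable ones, even when fasting does nothing.

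This is separate from the question of who chooses to fast in the first place. The switching follows events after fasting has begun, so baseline adjustment can remove only the part already visible at enrolment, for example in a first scan.

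At stake is the study's main message. The error leans towards reassurance about total fasting, and it can make partial fasting look like the harmful pattern. A larger sample would not reduce it.

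**Working it through.** **The plan's own figures.** The plan gives no figure for stopping or switching, so there is none to reproduce on this point. Its sample size serves only as a yardstick. With 159 women in three groups and alpha 0.05, the noncentral F gives power 0.805 when 0.25 is taken as Cohen's f, matching the stated 80%. The text labels the 0.25 as eta squared; that is a separate matter and does not affect what follows.

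**Inputs.** From the documents: three groups, 53 per group, grouping by days fasted. Assumed, because the documents give nothing:

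- p: share of women starting to fast who have an early growth or AFI concern, 10%
- birth-weight deficit in those women, 400 g
- sn: share of unaffected women who stop partway, 40%
- sa: share of affected women who stop partway, 40%, 60% or 80%
- true effect of fasting: none
- group A has the same 10% affected

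**Formulas.**

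- Affected share in B = p·sa / [p·sa + (1−p)·sn]
- Affected share in C = p·(1−sa) / [p·(1−sa) + (1−p)·(1−sn)]
- False difference in mean birth weight = 400 g × difference in shares

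**Birth weight.**

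| sa | Share in B | Share in C | C above B | C above A | B below A |
|---|---|---|---|---|---|
| 40% | 0.04/0.40 = 10% | 0.06/0.60 = 10% | 0 g | 0 g | 0 g |
| 60% | 0.06/0.42 = 14.3% | 0.04/0.58 = 6.9% | 29.6 g | 12.4 g | 17.1 g |
| 80% | 0.08/0.44 = 18.2% | 0.02/0.56 = 3.6% | 58.4 g | 25.7 g | 32.7 g |

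The first row shows the condition on which everything rests: equal stopping rates give no bias.

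**Scale.** Assume a birth-weight SD of 450 g (not in the documents). The standard error of a difference between two groups is 450 × √(2/53) = 87 g. The three-group ANOVA would reject in 5.9% of studies at sa = 60% and 8.5% at sa = 80%, against a nominal 5%. Across SDs of 400 to 500 g these become 5.7% to 6.1% and 7.8% to 9.4%. For comparison, f = 0.25 with evenly spaced means is a spread of 2 × 0.25 × 450/√(2/3) = 276 g between the extreme groups.

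**Symptoms.** Assume 30% of women who start fasting become symptomatic, and that 70% of these stop against 30% of the others.

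- B: 0.30×0.70 / (0.30×0.70 + 0.70×0.30) = 0.21/0.42 = 50%
- C: 0.30×0.30 / (0.30×0.30 + 0.70×0.70) = 0.09/0.58 = 15.5%

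With 53 per group that is about 26 against 8 women, an uncorrected chi-squared of about 14.0 (p < 0.001), although every woman started with the same risk.

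**Simulation as a check on direction.** Assumptions: SD 450 g; equal intended groups; half the effect of C in B; intended total fasters in the lowest fifth of birth weight stop with probability 0.2 to 0.6, the others with 0.05 to 0.1. Some 8% to 20% of intended total fasters then move to B.

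| True C−A | Observed C−A, stoppers placed in B |
|---|---|
| 0 g | +20 to +79 g |
| −100 g | −81 to −22 g |
| −200 g | −180 to −121 g |

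C versus A is pulled towards reassurance but keeps its sign. B versus C is more fragile: with a true C−A of −100 g, the true C−B of about −50 g appears as −10 to +89 g.

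**The case against.** **The documents do not show that women will stop for these reasons.** This stands. They give no stopping rates and do not say that scan findings are disclosed or lead to a change in fasting. The sentence on perceived harm reports a belief about not fasting, found in an earlier study. It continues with the view that fasting is safe in healthy pregnant women, who are the women recruited here, and the introduction stresses strong motives to keep fasting. The path is open, but how much it is used is unknown.

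**The effect on the primary outcome is small.** This largely stands. A false 12 to 26 g for C versus A is well inside the 87 g standard error. A reader might infer that a real harm of total fasting would be hidden or reversed on birth weight. The documents do not support that: there are no rates to base it on, and in the simulation C versus A keeps its sign when stoppers go to B. A change of sign in B versus C appears only under the more extreme assumed rates.

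**Symptoms are not a primary outcome.** True, and they are not among the secondary examples under Sample Size Justification. They are, however, listed first in the aim, and there the distortion can be large.

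**Movement into A.** A reader might infer that early stoppers carry harm into the non-fasting group. The text does not settle this. A woman who fasts 1 to 9 days fits no defined group, so she could be put in A, put in B or left out.

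**Intended fasting is a different question.** Partly stands. The aim is an association, in a study that calls itself exploratory. A woman enrolled late in Ramadan may already have stopped, so her stated intention can be affected too. This argues for adding the analysis rather than replacing the main comparison.

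**Conclusion.** The point holds as a conditional bias. As written, the plan lets early signs of the outcome influence the exposure group, and it collects nothing that would show whether this happened. If women with symptoms or worrying findings stop more often than others, C looks falsely better and B falsely worse.

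The direction follows from the design; the size rests wholly on assumed stopping rates. Under those shown it is modest for birth weight and potentially large for hypoglycaemic symptoms. It would go too far to read the plan as leaving in C only women with reassuring findings, or as letting the outcome determine the group: in the illustrations 20% to 40% of women with a growth or AFI concern, and 30% of symptomatic women, remain in C.

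Severity: should be fixed. Confidence is high in the description of the design, and lower in the presence and size of the bias.

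**What to change.** 1. At enrolment, record each woman's intended fasting for the month (none, some days, all days) and her fasting so far.
2. During follow-up, record days fasted and the date and main reason for any stop (symptom, scan finding or advice, other).
3. State how women fasting 1 to 9 days, and more than 20 but not all days, are classified.
4. Keep the completed-days comparison. Add one pre-specified analysis, either by intended or started fasting at enrolment, or returning women who stopped for symptoms or scan findings to their starting group.
5. Do not interpret B versus C as a dose effect unless the analyses agree.

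The cost is a few extra history questions and one extra analysis. The intended-fasting contrast is diluted by ordinary non-adherence and is imperfect for women enrolled late in Ramadan. Intention and reasons need to be captured prospectively, because they cannot be recovered reliably afterwards. The change concerns data and analysis only.

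### Entry has no upper gestational limit, so women enrolled past the preterm cut-off count as PTL non-events by construction; this dilutes the PTL rate and its power, and can create or hide a group difference if gestation at entry is unequal

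*Combined protocol and SAP*

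**What the plan says.** The combined protocol and SAP bears on this point in five places.

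- **Inclusion criteria:** "3rd trimester pregnancy (starting from 28 weeks"), dated by last menstrual period and confirmed by ultrasound. Neither the inclusion nor the exclusion list gives a maximum gestation.
- **Type of the study, Duration of the setting and Population:** a "Prospective Comparative Cohort Study" set in "The Holy month of Ramadan (from 18th June To 16th July 2015"). On group formation: "The patients will be recruited from outpatient clinic during Ramadan then followed during the holy month then grouped into three groups". Group B is the "Partially fasting group (average days of fasting 10-20 day").
- **Sample Size Justification, outcomes:** "The secondary outcome measures are the incidence of unwanted fetal outcomes (e.g., IUGR, PTL, or NICU admission"). PTL has no definition and no at-risk denominator.
- **Sample Size Justification, power:** 159 women give 93% power for IUGR, PTL and NICU admission at w = 0.3, using a two-sided chi-squared test at 0.05.
- **Statistical Methods:** "Categorical data will be compared using the chi-squared test, or Fisher's exact test when appropriate". There is no adjustment or stratification for gestation at entry.

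**The concern.** A woman first seen at 38 weeks is eligible. If preterm means before 37+0 weeks, she had passed the risk period before she joined, so she is a PTL non-event whatever she does about fasting. Putting her in the right fasting group does not help, because she cannot have the event in any of them. Women who enter below the cut-off also differ in exposure: entry at 28 weeks leaves 9 weeks at risk, and entry at 36 weeks leaves 1. The planned test treats all of them alike.

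Two things are at stake. The reported PTL incidence is not the incidence among women who could have had the event, and the power statement counts women who carry no information on PTL. In addition, the group proportions depend on each group's gestation mix at entry, which nothing in this non-randomised design balances. Women choose whether to fast. A woman who enters late and delivers early in the month also has fewer days in which to meet the definition of group B or C.

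**Working it through.** **Inputs from the plan:** N = 159 (53 per group), w = 0.3, alpha 0.05, three groups, entry from 28 weeks.

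**Assumptions (not in the plan):** cut-off 37+0 weeks; the distribution of gestation at entry; PTL risk r among women still at risk; share s of each group enrolled past the cut-off.

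**1. The plan's power figure.** Noncentrality = N × w² = 159 × 0.09 = 14.31. With 2 degrees of freedom the power is 93.3%, so the stated 93% reproduces, with all 159 women counted as able to have PTL.

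**2. Share not at risk.** If entry were uniform over 28–40 weeks, s = (40 − 37)/(40 − 28) = 25%. Then 0.25 × 159 ≈ 40 women are not at risk and about 119 are.

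**3. Power on the at-risk women.** 119 × 0.09 = 10.71, which gives about 84% at the same w.

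**4. Dilution with equal shares.** Observed rate = r × (1 − s), so r = 10% is reported as 0.10 × 0.75 = 7.5%. If the true at-risk risks are 5%/15%/30%, the observed rates are 3.75%/11.25%/22.5%. Then w falls from 0.276 to 0.233, and power at N = 159 falls from 88.5% to 75.2%. Restricting to the 119 at-risk women restores w = 0.276 but gives only 77.3% power: the restriction corrects the rate and does not bring back the missing information.

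**5. False difference with unequal shares.** There is no fasting effect and r is the same in A, B and C. The table gives the simulated rejection rate of the planned chi-squared test at 53 per group.

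| Share past cut-off, A/B/C | r | Observed PTL, A/B/C | Rejection |
|---|---|---|---|
| 25/25/25% | 10% | 7.5/7.5/7.5% | about 4.5% |
| 40/25/10% | 10% | 6/7.5/9% | about 7% |
| 40/20/0% | 5% | 3/4/5% | 5.4% |
| 40/20/0% | 10% | 6/8/10% | 8.7% |
| 40/20/0% | 20% | 12/16/20% | 15.5% |
| 60/30/0% | 10% | 4/7/10% | 15.5% |
| 60/30/0% | 20% | 8/14/20% | 33.2% |

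With equal 25% shares, rejection stayed between 3.9% and 5.1% for r from 5% to 20%.

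**6. Masking.** Suppose 10% of A and 40% of C enter past the cut-off, and the at-risk risks are 10% in A and 15% in C. The observed rates are 0.10 × 0.90 = 9% and 0.15 × 0.60 = 9%, so a real increase disappears.

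**7. Late entry below the cut-off.** With a constant weekly hazard that gives 10% over weeks 28–37 (assumption), the remaining risk is 10% from 28 weeks, 5.7% from 32, 3.5% from 34 and 1.2% from 36. The flat r used in steps 4–6 ignores this gradient, which is a reason to account for gestation at entry as well as to restrict the denominator.

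**The case against.** **The size is not known.** The plan gives no PTL rate and no gestation distribution. Uniform entry to 40 weeks ignores the fact that women deliver from 37 weeks on, and very late entrants may be hard to place in B or C at all. The 25% could be too high. This stands: the figures are illustrations.

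**A false difference needs imbalance.** With equal shares there is none, and a 6% versus 9% contrast at 53 per group is about 3.2 versus 4.8 women, which the planned test flags only about 7% of the time. This also stands. A reader might infer that the plan will produce a spurious PTL effect of fasting. The documents do not support that, because they say nothing about how gestation at entry differs between groups. The rejection rates of 15–33% need extreme shares or a 20% risk.

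**A delayed-entry survival analysis looks like the natural repair.** It is not safe as a simple substitution. Groups are assigned from fasting done after enrolment. If only days fasted while pregnant count, a woman who delivers preterm soon after entry cannot reach B, and may not reach C. A clock that starts at enrolment would then build event-free time into the fasting groups. Events would also be few: 10% of 119 is about 12 across three groups.

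**PTL is a minor outcome.** It is listed as an example among the secondary outcomes of a study that calls itself exploratory, and it is not named in the aim or the study question. This limits the weight of the point. It does not remove it, since the plan states a power for PTL by name.

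**Conclusion.** The point holds for PTL. With a lower gestational bound only and a denominator of all women, anyone enrolled past the cut-off is a built-in non-event. Dilution of the rate and of power follows whenever such women are enrolled. If they are 25% of the sample, about 119 of 159 remain at risk and 93% power becomes about 84% at w = 0.3. A produced or masked group difference is possible, and it depends on unequal gestation at entry. In moderate scenarios at a 10% risk the false-positive rate is about 7–9% instead of a nominal 5%.

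A reader might extend this to the primary result. The documents do not support that: the denominator problem is specific to an event that can happen only before a given gestation, and birth weight can be measured in women enrolled at any gestation. The change should be made, but it concerns one secondary, exploratory outcome.

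**What to change.** 1. Define PTL by a stated gestational cut-off and add gestation at delivery to the data items. The Methodology section lists neither, although follow-up runs to delivery.
2. Restrict the PTL denominator to women enrolled before the cut-off. Keep all women for birth weight and NICU admission.
3. Stratify or adjust the PTL comparison for gestation at entry, in broad bands because events will be few.
4. Report gestation at entry by fasting group, including the number enrolled past the cut-off.
5. Restate the PTL power for the smaller denominator.
6. Use a delayed-entry time-to-event analysis only if fasting group is handled as time-varying, or if the clock starts after group has been determined. The second option leaves out events that occur before that point.

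**Cost:** a definition, one added data item and revised analysis text; recruitment does not change. The PTL denominator is smaller and its stated power lower. Steps 1–5 do not remove the separate difficulty that group is assigned from fasting after enrolment, and the report should say so.

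### No step keeps fasting status from the person scanning, so fetal growth, AFI and any scan-based IUGR count are open to differential measurement

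*Combined protocol and SAP*

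**What the plan says.** The study is a "Prospective Comparative Cohort Study" with one named setting, the "EL- Demerdash outpatient clinic" (Type of the study; Study setting). Women are recruited there and "followed during the holy month then grouped into three groups A ,B, C regarding fasting state" (Population). The Study question asks "does fasting during the holy month of Ramadan has a poor obstetric outcome", so the direction of expectation is on record.

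Methodology item 1 is a history, taken for the present pregnancy "with special emphasis on signs & symptoms of hypoglycemia in the form of fatigue, dizziness, fainting, blurred vision, vomiting". Fasting is not among its listed items. Item 3 is "Ultrasound fetal biometry every 2 weeks till delivery looking for" fetal biometry, AFI and Doppler. Item 4 is weight after delivery.

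The Aim of the Work names hypoglycaemic symptoms, fetal growth and AFI among the outcomes. The Sample Size Justification states: "The primary outcome measure is the difference between the three study groups as regards the fetal birth weight". It gives the secondary outcomes as "the incidence of unwanted fetal outcomes (e.g., IUGR, PTL, or NICU admission", without diagnostic definitions.

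Masking of sonographers, outcome assessors or analysts is not mentioned. Nor is it stated who takes the history, who records fasting days or who scans.

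**The concern.** Women cannot be masked to their own fasting, so in a cohort like this the available protection lies with the person who measures. Biometry and AFI depend on the operator. A reader who knows that a woman is fasting, in a study asking whether fasting does harm, may measure or classify borderline findings differently from the way the same findings would be recorded in a woman who is not fasting.

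The error would then differ between groups. The planned ANOVA, Kruskal-Wallis and chi-squared comparisons cannot detect or remove an error of that kind. Growth, AFI and a scan-based IUGR label would also share it, so agreement between them would be weaker evidence than it appears.

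**Working it through.** **1. The plan's own figure.** The nearest stated figure is 93% power for the secondary outcomes, IUGR among them. Inputs from the Sample Size Justification: N = 159, w = 0.3, two-sided alpha 0.05. Three groups by yes/no gives 2 degrees of freedom. Noncentrality = N × w² = 159 × 0.09 = 14.31; critical value 5.99; power 93.3%. The figure reproduces. It takes for granted that events are counted in the same way in every group.

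**2. The text side by side.**

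| Question | What the plan states |
|---|---|
| Who scans? | Not stated |
| Who records fasting, and where? | Not stated |
| Is the scan reader masked? | Not stated; no step described |
| Is IUGR taken from scans or from birth weight? | Not stated |
| When is the fasting group known? | After follow-up through the month (18 June to 16 July 2015) |
| When do scans stop? | At delivery |

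Entry is from 28 weeks. A woman at 28 weeks on 18 June is at 32 weeks on 16 July, 28 days later. Her two-weekly scans then go on until delivery with her fasting group already settled. For scans during the month the final group is not fixed, but whether she is currently fasting can be known.

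**3. Distortion of an estimate (assumed figures; only n = 53 comes from the plan).** Suppose true IUGR is 8% in every group: 0.08 × 53 = 4.24, about 4 cases. Suppose three more borderline fetuses are labelled in group C.

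- Group A: 4/53 = 7.5%. Group C: 7/53 = 13.2%. Ratio 7/4 = 1.75.
- A against C: Fisher p = 0.53; uncorrected chi-squared p = 0.34.
- Three groups, with B anywhere from 4 to 7 cases: p about 0.52 to 0.63; w about 0.08 to 0.09, against the planned 0.3.

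The estimate moves and the test does not reject.

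**4. Effect on the error rate (assumed; no true difference, 53 per group, three-group chi-squared test, simulated).** Over-calling is in percentage points above the true rate.

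| True IUGR rate | +2.5 in B, +5 in C | +5 in B, +10 in C |
|---|---|---|
| 5% | 11.5% | 30.1% |
| 10% | 9.4% | 22.9% |
| 15% | 8.5% | 19.1% |

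With no over-calling the same simulation rejects in 4.0% to 5.0% of trials.

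**5. AFI (assumed graded shift of 0, d/2 and d SD in A, B and C).** The variance of the three means is d²/6, so noncentrality = 159 × d²/6, tested on F with 2 and 156 degrees of freedom.

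- d = 0.1: noncentrality 0.265, rejection rate 7.0%
- d = 0.2: noncentrality 1.06, rejection rate 13.6%
- d = 0.3: noncentrality 2.385, rejection rate 25.8%

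**The case against.** The strongest reply is that the plan is silent rather than wrong. A reader might infer that the staff who ask about fasting also scan, unmasked. The documents do not say so. One setting is named, but roles are not, fasting is not a listed history item, and the sentence about hypoglycaemic symptoms concerns neither fasting status nor scanning. This stands: the point is the missing step, not a demonstrated unmasked reading.

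Second, a reader might infer that IUGR is a scan label. It is undefined and could as well be judged from the weight after delivery, so the concern reaches IUGR only conditionally.

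Third, women are grouped after the month, so scans during Ramadan precede final grouping. That is true, but it neither prevents awareness of current fasting nor protects later scans.

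Fourth, every rate in steps 3 to 5 is assumed, and the 4 against 7 example is far from significant. This stands too. The figures show how the mechanism works and how sensitive the tests are to it. They do not estimate bias in this study.

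Fifth, the study calls itself exploratory and its primary outcome is a weight. That limits the weight of the point, but growth and AFI are stated aims, and IUGR has its own power claim.

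**Conclusion.** The point holds in limited form. In a single-clinic cohort with a question directed at harm, the plan schedules repeated operator-dependent scans and describes no step to keep fasting status from the reader. Fetal growth and AFI are exposed, and IUGR is exposed if it comes from the scans.

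The size cannot be derived from the documents. Under assumed over-calling of 2.5 and 5 points, the false-positive rate for IUGR would be about 8.5% to 11.5% instead of 5%; under 5 and 10 points, about 19% to 30%. The 4/53 against 7/53 example shows a ratio of 1.75 with no true effect, and nothing more.

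Two further readings should be resisted. One is that birth weight is wholly immune: its measurement is largely protected, but if scan findings led to earlier delivery the weight itself could change. The other is that such a chain, on to mode of delivery or NICU admission, is established: the plan contains no rule linking scan findings to delivery or admission, so it remains a possibility. It is worth changing the conduct of the study for the scan outcomes. The point is no reason to distrust the measurement of the primary outcome.

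**What to change.** Add a short paragraph to the Methodology, to be carried out with existing staff:

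- State who scans and who records fasting days. Where possible these should be different members of the existing staff.
- Keep the fasting record on a form separate from the scan request and the scan record.
- At every visit, enter the scan measurements before any fasting or symptom enquiry, and ask women not to mention fasting during the scan.
- Log each occasion when the reader learned the fasting status, and report incomplete masking as a limitation.
- State in advance the measured criterion by which IUGR is counted, so that it is not an unmasked impression.

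The choice of criterion is for the investigators. Deriving IUGR from birth weight for gestational age would avoid the scan, but it would make a secondary outcome largely a function of the primary one and would need a named growth reference. The masking steps do not depend on that choice.

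The cost is one extra form, a fixed order at each visit and a definition. No new assessor or procedure is needed. The protection is partial: women may volunteer their status, and at repeat visits the reader may remember it from the last one, which is why the log is needed.
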